11.6.1 Treatment Modification Guidelines

The dose of ADXS11-001 will not be modified (e.g., reduced or increased). However, treatment may be delayed or discontinued for drug related severe and life-threating toxicities, as shown below in Table 11.

Table 11 Treatment Delay/Discontinuation Guidelines for Drug-Related Adverse Events

Toxicity	Grade	Hold treatment	Timing for restarting treatment	Discontinue Treatment
	1,2,3	No	N/A	N/A
Hematologic	4	Yes	Toxicity resolves to ≤Grade 1 or baseline	Toxicity does not resolve to ≤Grade 1 or baseline within 12 weeks
	1	No	N/A	N/A
Non- hematologic, excluding cytokine release symptoms and DLTs	2-3	Yes	Toxicity resolves to ≤Grade 1	Toxicity not resolved to ≤Grade 1 within 12 weeks of last infusion ^a
	4	N/A	Permanent treatment discontinuation	Permanent Discontinuation from Treatment

^a With investigator and sponsor agreement, subjects with a non-hematologic AE (e.g. alopecia, neuropathy) still at grade 2 after 12 weeks, may continue treatment if only asymptomatic and controlled.

11.6.2 ADXS11-001 Treatment Alterations

Subjects who experience a DLT during the dose escalation portion of the study or experience events described as a DLT in any subsequent treatment cycle will be discontinued from study treatment. However, if the subject who experienced a DLT shows significant response to ADXS11-001, they may be eligible to receive ADXS11-001 at a lower dose level for subsequent doses and cycles following discussion and agreement between the Investigator and Sponsor. See Section 6.1 Dose Limiting Toxicity Criteria for definition of DLT.

11.7 Major and Minor Surgeries and ADXS11-001 Treatment

No formal studies of the effect of ADXS11-001 on wound healing have been conducted. However, based on its mechanism of action it is not expected that administration of ADXS11-001 would complicate wound healing. Therefore, a subject may initiate or resume study treatment 2 weeks after minor surgery (i.e., surgery involving little risk to the life of the subject; specifically an operation on the superficial structures of the body or a manipulative procedure that does not involve a serious risk) if the wound has completely healed and there are no wound healing complications. A subject who has wound healing complications following minor surgery, received major surgery or requires new implants and/or devices (permitted by the protocol) during the course of the study, must wait a minimum of 6 weeks and must have recovered from any toxicity (e.g., return to baseline or Grade 1) and/or complication before the next infusion of study treatment. Sponsor consultation is required prior to resuming study treatment for these subjects. If the treatment is delayed due to concomitant surgery beyond 12 weeks, the subject may be discontinued from the study.

11.8 Discontinuation of Study Subjects

11.8.1 Subject Study Discontinuation Criteria

Subjects may withdraw consent at any time for any reason or be discontinued from the trial at the discretion of the investigator, should any untoward effect occur. In addition, a subject may be withdrawn by the investigator or the sponsor if enrollment into the trial is inappropriate, the trial plan is violated, or for administrative and/or other safety reasons.

A subject may be discontinued from the trial for any of the following reasons:

- Screen Failure
- AE/SAE
- Lost to Follow-Up
- Disease Progression
- Death
- Withdrawal of Consent by Subject
- Investigator Decision/Study Non-Compliance by Subject
- Achieved Complete Remission
- Completed Study (at least 24 months of study treatment)
- Other (specify)

In all cases, the reason for and date of withdrawal must be recorded in the eCRF and in the subject's medical records. The subject must be followed up to establish whether the reason was an AE, and, if so, this must be reported.

When a subject discontinues/withdraws prior to study completion, all applicable activities scheduled for the final assessment (End of Therapy assessments) should be performed at the time of discontinuation. Any AEs that are present at the time of discontinuation/withdrawal should be followed in accordance with the safety requirements outlined in Section 13.2 Collection of Safety Information.

The Investigator must make every effort to contact subjects who discontinue the study prematurely or are lost to follow-up and to schedule the end of therapy assessments. Attempts to contact such subjects must be documented in the subject's records (e.g., times and dates of attempted telephone contact, receipt for sending a registered letter).

11.8.2 Suspension or Discontinuation of the Study

The occurrence of any Grade 4 (life threatening) toxicity may result in the temporary suspension of the study to evaluate available safety information to justify continued enrollment of subjects into the study.

The study may be stopped at the study center at any time by the investigator. Advaxis may stop the study (and/or the study center) for any reason.

12 CONCURRENT THERAPIES AND PROCEDURES

All prescription and nonprescription medication (excluding vitamins, nutritional supplements and hormone replacement therapy) taken by the subject from 30 days prior to screening and up to and including completion of the 3-year Lm surveillance period will be recorded in the medical record and on the eCRF. Any addition, deletion, or change in the dose of these medications will also be recorded. Generic names should be used to eliminate confusion that may result from trade names. Protocol-mandated prophylactic medications, antibiotics and procedures administered/performed following the completion of study treatment, including during the 3-year Lm surveillance period, should also be captured in the eCRF.

Study subjects should be reminded that acetaminophen should not be used for pretreatment prophylaxis associated with the foreseeable AEs related to the study treatment since this medication can interfere with treatment.

Medications specifically prohibited in the exclusion criteria are not allowed during the ongoing trial. If there is a clinical indication for one of these or other medications specifically prohibited during the trial, discontinuation from trial therapy may be required. The Investigator should discuss any questions regarding this with the Sponsor. The final decision on any supportive therapy rests with the Investigator and/or the subject's primary physician. However, the decision to continue the subject's on-trial therapy requires the mutual agreement of the Investigator, the Sponsor, and the subject.

Subjects are prohibited from receiving the following therapies during the screening and treatment phases (including retreatment for post-complete response relapse) of this trial:

- Anti-cancer systemic chemotherapy or biological therapy
- Surgical treatment as per consultation with the sponsor
- PI3K and TNFα inhibitors
- Immunotherapy not specified in this protocol
- Investigational agents other than ADXS11-001
- Radiation therapy (except palliative radiation therapy for disease-related pain with a consult with the sponsor's medical monitor)
- Live vaccines within 30 days prior to the first dose of trial treatment and while participating in the trial. Examples of live vaccines include, but are not limited to, the following: measles, mumps, rubella, chicken pox, yellow fever, rabies, BCG, and typhoid (oral) vaccine. Seasonal influenza vaccines for injection are generally killed virus vaccines and are allowed; however, intranasal influenza vaccines (e.g., Flu-Mist®) are live attenuated vaccines and are not allowed.
- Acetaminophen is not to be used for premedication but may be used for supportive care measures. NSAIDs, such as naproxen and ibuprofen have been evaluated and are confirmed not to interfere with efficacy.

Subjects who, in the assessment by the Investigator, require the use of any of the aforementioned treatments for clinical management should be removed from the trial. Subjects may receive other medications that the Investigator deems to be medically necessary.

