5 SUBJECT SELECTION

5.1 Inclusion Criteria

- 1. Subject is at least 18 years of age or older on day of signing informed consent
- 2. Subject has histologically-confirmed, persistent, metastatic or recurrent squamous or non-squamous cell carcinoma, adenosquamous carcinoma, or adenocarcinoma of the cervix with documented disease progression (disease not amenable to surgery or standard radiotherapy).
- 3. Subject may have received ≤2 regimens for disease in the metastatic setting. Subjects who have had >2 prior treatment regimens in the metastatic setting MAY be eligible only after consultation with the investigator and the sponsor, and providing all other inclusion/exclusion criteria have been met. Subjects must have either documented disease progression OR become intolerant to prior therapy, in the metastatic setting.
- 4. Subject has measurable and/or evaluable disease for response assessment per RECIST 1.1. Tumors within a previously irradiated field will be designated as "non-target" lesions unless progression is documented or a biopsy is obtained to confirm persistence at least 90 days following completion of radiation therapy.

- 5. Subject is able to provide written informed consent.
- 6. Subject demonstrates adequate organ function as defined in Table 3. All screening laboratory testing should be performed within 3 days of treatment initiation.

Table 3 Adequate Organ Function Laboratory Values

System	Laboratory Value							
Hematologic								
Absolute neutrophil count (ANC) ^a	≥1,000 /mcL							
Platelets	≥75,000 / mcL							
Hemoglobin	≥9 g/dL or ≥5.6 mmol/L							
Renal								
Serum creatinine OR	≤1.5 X upper limit of normal (ULN) OR							
Measured or calculated ^b creatinine clearance								
(GFR can also be used in place of creatinine or CrCl)	≥50 mL/min for subject with creatinine levels >1.5 X institutional ULN							
Hepatic								
	≤1.5 X ULN OR							
Serum total bilirubin	Direct bilirubin ≤ULN for subjects with total bilirubin levels >1.5 ULN							
AST (SGOT) and ALT (SGPT)	≤2.5 X ULN OR							
AST (SOOT) and ALT (SOFT)	≤5 X ULN for subjects with liver metastases							
Coagulation								
International Normalized Ratio (INR) or Prothrombin Time (PT)	≤1.5 X ULN unless subject is receiving anticoagulant therapy as long as PT or INR is within therapeutic range of intended use of anticoagulants							

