5.2 Exclusion Criteria

- 1. In the opinion of the investigator, subject has rapidly progressing disease, OR has life expectancy of less than 6 months, OR would be unable to receive at least 1 cycle of therapy.
- 2. Subject has received chemotherapy and/or radiation therapy (except palliative radiation therapy for disease-related pain) within ≤2 weeks of first ADXS11-001 infusion.
- 3. Subject has not recovered (i.e., Grade ≤1 at baseline) from AEs, with the exception of alopecia due to previously administered agent(s).
- 4. Subject has a known additional malignancy that is progressing or requires active treatment. Exceptions include basal cell carcinoma of the skin, squamous cell carcinoma of the skin, or *in situ* cervical cancer that has undergone potentially curative therapy.
- 5. Has an active autoimmune disease requiring systemic treatment within the past 3 months or a documented history of clinically severe autoimmune disease, or a syndrome that requires systemic steroids or immunosuppressive agents. Subjects with vitiligo or resolved childhood asthma/atopy would be an exception to this rule. Subjects that require intermittent use of bronchodilators or local steroid injections would not be excluded from the study. Subjects with hypothyroidism stable on hormone replacement or Sjorgen's syndrome will not be excluded from the study.
- 6. Has neuropathy (sensory and motor) ≥Grade 3 per CTCAE v 4.03.
- 7. Subject has diagnosis of immunodeficiency, is dependent on or has received systemic steroid therapy or any other form of immunosuppressive therapy within 7 days prior to the first dose of trial treatment with the exception of topical corticosteroids and occasional inhaled corticosteroids, as indicated.
- 8. Subject has known active central nervous system (CNS) metastases and/or carcinomatous meningitis. Subjects with previously treated brain metastases may participate provided they are stable (without evidence of progression by imaging for at least 4 weeks prior to the first dose of trial treatment and any neurologic symptoms have returned to baseline), have no evidence of new or enlarging brain metastases, and are not using steroids for at least 7 days prior to trial treatment.

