9.1.10 Best Overall Response (RECIST 1.1)

The best overall response is the best response recorded from the start of the study treatment until the end of treatment taking into account any requirement for confirmation. The subject's best overall response assignment will depend on the findings of both target and non-target disease and will also take into consideration the appearance of new lesions (Table 7).

Table 7 Best Overall Response (RECIST 1.1)

Target Lesions	Target Lesions Non-Target Lesions		
Baseline (Index) and New Measurable Lesions	Baseline Lesions	Baseline Lesions Unequivocal New Lesions	
CR	CR	No	CR
CR	Non-CR/Non-PD	No	PR
CR	NE	No	PR
PR	Non-PD or NE	No	PR
SD	Non-PD or NE	No	SD
Not all evaluated	Non-PD	No	NE
PD	Any	Yes or No	PD
Any	PD	Yes or No	PD

a Subjects with an initial finding of progressive disease (irPD) before or at the 12-week imaging assessment, but without rapid clinical deterioration, require confirmation of irPD with a second, consecutive scan obtained ≥ 4 weeks from the initiation documentation. Subjects will continue to receive study treatment until irPD is confirmed at this later time point. Best overall response (BOR) will therefore include responses occurring at any time before disease progression and after early progression (i.e., within the first 12 weeks of the study).

Target Lesions	Non-Target Lesions		
Baseline (Index) and New Measurable Lesions Baseline Lesions		Unequivocal New Lesions	Overall Response
Any	Any	Yes	PD

CR = complete response; NE = not evaluable at a particular time point; PR = partial response; SD = stable disease; PD = progressive disease

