9.1.11 Immune-Related Best Overall Response (irRECIST)

The immune-related best overall response (irBOR) is the best irRC overall response over the study as a whole, recorded between the date of first dose until the last tumor assessment prior to subsequent therapy (including tumor resection surgery) for the individual subject in the study (Table 8). As with the primary definitions of tumor response, early progression (i.e., irPD occurring prior to Week 12) will not preclude an irBOR of irCR, irPR or irSD resulting from the Week 12 assessment. An assessment of irPD at or after Week 12 will preclude a subsequent irBOR of irCR, irPR or irSD. However, any post-progression clinical activity in subjects with irBOR of irPD may be summarized for exploratory purposes.

Table 8 Immune-Related Best Overall Response (irBOR)

Target Lesions Baseline (Index) and New Measurable Lesions Non-Target I		Lesions ^a	
Total Measurable Tumor Burden	Baseline Lesions	Unequivocal New Lesions	irRC Overall Response
irCR	irCR	No	irCR
irCR	irSD	No	irPR
irPR	irCR or irSD	No	irPR
irSD	irCR or irSD	No	irSD
irPD	Any	Yes or No	irPD
Any	Unequivocal Progression	Yes or No	irPD
Any	Any	Yes	irPD

irCR = immune-related complete response; irPR = immune-related partial response; irSD = immune-related stable disease; irPD = immune-related progressive disease

^a Any increase in the size or number of non-measurable lesions does not necessarily imply an overall response of irPD. If these lesions become measurable (≥10 mm) at a subsequent assessment, their measurement will at that point start to contribute to the total measurable tumor burden. To achieve unequivocal progression of non-target lesions, there must be substantial worsening in non-target disease that is of a magnitude that the Investigator feels it is important to change therapy. Equivocal findings of progression of non-target lesions (e.g., small and uncertain new lesions; cystic changes or necrosis in existing lesions) should be considered irSD, and treatment may continue until the next assessment.

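### Palliative radiation for pain is permitted during treatment, but no response rule says how a target lesion irradiated after the baseline scan is handled, so radiation shrinkage can count as response to ADXS11-001

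*Combined protocol and SAP*

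**What the plan says.** **Therapy rules.** Section 12 opens its list with "Subjects are prohibited from receiving the following therapies during the screening and treatment phases". One entry carries an exception: "Radiation therapy (except palliative radiation therapy for disease-related pain with a consult with the" sponsor's medical monitor). Nothing requires the irradiated lesion to be non-target. Exclusion criterion 2 has a parallel exception for the period before the first infusion: "except palliative radiation therapy for disease-related pain) within" 2 weeks. Surgery is in the same Section 12 list, worded as "Surgical treatment as per consultation with the sponsor".

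**Response rules.** Section 9.1.4 fixes the target lesions and the reference sum at baseline. Section 9.1.5 defines partial response as a fall of at least 30% in that sum. Section 9.1.6 applies the same 30% to total measurable tumor burden. Neither makes an exception for a lesion treated locally. For RECIST 1.1, Section 9.1.10 says "The best overall response is the best response recorded from the start of the study treatment until the end of treatment". For irRECIST, Section 9.1.11 runs from first dose "until the last tumor assessment prior to subsequent therapy (including tumor resection surgery) for the individual subject in the study".

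**Earlier radiation.** Inclusion criterion 4 begins "Tumors within a previously irradiated field will be designated as" non-target, unless progression or biopsy-confirmed persistence is shown. Section 9.1.3 treats lesions in a previously irradiated area as non-measurable unless they are new.

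**Analysis.** Section 14.5.5 defines the response rate, durations and PFS without mentioning local therapy. Subjects who have not progressed are censored only at discontinuation or study completion.

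**The concern.** Inclusion criterion 4 and Section 9.1.3 show that the authors saw the problem with irradiated lesions: a change in size after radiation says little about the drug. Those provisions deal with lesions irradiated earlier. They do not say what to do when a lesion already chosen as a target is irradiated during treatment, which Section 12 allows.

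The study has no control arm, and further assessment of the recommended dose is meant to cover clinical activity as well as safety. Without a rule fixed in advance, a response produced by radiation cannot be separated cleanly from one produced by ADXS11-001. With about 15 subjects at that dose, one such response is visible in the reported rate.

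**Working it through.** The plan states no figure on this point and has no power calculation, so there is nothing to reproduce. The check is a reading of the rules followed by arithmetic for scale. Lesion sizes below are assumed. The 30% and 20% thresholds come from Sections 9.1.5 and 9.1.6, and the number at the recommended dose, about 15, from Section 14.3.

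**1. Can the case arise under the text?** Three steps are needed. Radiation for pain is permitted during treatment (Section 12). The target list and reference sum stay as set at baseline (9.1.4). Any fall of at least 30% up to the end of treatment counts (9.1.5, 9.1.10). No passage interrupts the chain.

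**2. One lesion can make a partial response.** Targets 60 + 40 = 100 mm. The first is irradiated and shrinks to 30 mm; the second is unchanged. Sum = 30 + 40 = 70 mm; change = 70/100 − 1 = −30%, a partial response under both criteria. Without the irradiated lesion the change is 40/40 − 1 = 0%, stable disease.

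**3. How much shrinkage is needed?** If the treated lesion is a share s of the baseline sum and the others do not change, it must shrink by 0.30/s:

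| Share of baseline sum | Shrinkage needed in that lesion |
|---|---|
| 30% | 100% |
| 40% | 75% |
| 50% | 60% |
| 60% | 50% |

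The lesion must therefore be a large part of the sum and respond well.

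**4. Effect on the response rate.** Each case adds 1/15 = 6.7 points. Exact (Clopper-Pearson) 95% intervals: 0/15 = 0% (0 to 21.8); 1/15 = 6.7% (0.2 to 31.9); 2/15 = 13.3% (1.7 to 40.5). Section 14.5.5 counts only subjects who complete a cycle, so the denominator may be smaller; at 12 it is 1/12 = 8.3 points.

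**5. Progression: the direction is not fixed.**
- Masked: 60 to 30 mm and 40 to 52 mm gives 82 mm, −18%, stable disease, although the untreated lesion grew by 52/40 − 1 = 30%.
- Brought forward: after step 2 the smallest sum is 70 mm, so the progression threshold falls from 1.2 × 100 = 120 mm to 1.2 × 70 = 84 mm. With the first lesion at 30 mm, the second needs to reach only 84 − 30 = 54 mm. Had the first stayed at 60 mm, the second would have needed 120 − 60 = 60 mm.

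**The case against.** **Subjects who need a listed therapy leave the trial.** Section 12 says that those who "require the use of any of the aforementioned treatments for clinical management should be removed from the trial". This does not naturally reach palliative radiation, which is carved out of its own list entry; applying removal to it would empty the exception.

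**Exposure is narrow.** Bone lesions are non-measurable (9.1.3). Many subjects will have had chemoradiation, so lesions in that field are often already non-target. RECIST 1.1 best response ends with treatment. All of this stands: it limits how often the case arises but does not close the gap.

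**Radiation between the baseline scan and first infusion is covered.** Inclusion criterion 4 refers to a previously irradiated field, and eligibility is checked again before the Week 1 infusion. That reading is reasonable, so this window is a matter of clarification.

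**Affected subjects can be found later.** On-study procedures are documented (Table 5), scans must be available for independent review (Section 15.4), and Table 7 has a not-evaluable row for incompletely evaluated targets. These make a rule easy to apply but do not supply one.

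**Stronger readings that the documents do not support.** A reader might infer that on-study surgery is plainly allowed. It sits in the prohibited list with ambiguous wording; Section 12 calls for removal, while Section 11.7 lets treatment resume after surgery without distinguishing tumor resection. A reader might also infer that irRECIST is already protected and only RECIST 1.1 is exposed. The cut in Section 9.1.11 names resection, not radiation; palliative radiation during continuing treatment may not be subsequent therapy, and 9.1.6 excludes no irradiated lesion.

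**Conclusion.** The gap is real for radiation and applies to both response systems. As written, an irradiated target lesion can turn stable disease into a partial response, worth 6.7 points of response rate per case at 15 subjects. This requires that the lesion is a target, that it shrinks by the amounts in the table above while the others hold steady, and that the subject stays on treatment.

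The documents give no frequency for on-study radiation, so no expected number of affected subjects, and no total inflation, can be stated. It is also tempting to conclude that PFS and duration of response are inflated. That is not shown: radiation can mask growth, but it also lowers the smallest sum and so the progression threshold. Response is a secondary endpoint, summarized descriptively with no hypothesis test. The point merits a short, definite correction; it does not threaten the primary safety objective.

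**What to change.** In Sections 9.1.5, 9.1.6, 9.1.10, 9.1.11 and 14.5.5, state one rule for RECIST 1.1 and irRECIST:

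- A target lesion treated locally after the baseline scan, including between that scan and the first infusion, is not evaluable from the treatment date and cannot contribute to a decrease.
- Later time-point responses are not evaluable unless progression is shown elsewhere under the criteria in question. Say how the remaining target lesions are assessed for this.
- Best overall response uses only assessments made before the local therapy.
- Section 14.5.5 says how these subjects enter duration of response, duration of stable disease and PFS, consistently with the points above.

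Record the lesion's identity and the treatment date on the existing eCRF page for procedures.

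Separately, Section 11.7 and the two statements in Section 12 (the prohibited list and the removal sentence) must be reconciled on whether a subject may have on-study surgery and continue. Whatever is decided, the same analysis rule would apply to a resected target lesion.

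The cost is a few sentences and one or two data fields. A few subjects may become not evaluable, and the reported response rate may be slightly lower. The rule governs analysis only and does not change who may receive radiation.
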